#### 6.5.2.1 Liver Safety Assessment

The liver safety assessments will be summarized by the categories below based on the measurements from Alkaline Phosphatase (ALP), Alanine Transaminase (ALT), total bilirubin, Aspartate Transaminase (AST) and their combination. These parameters will be based on measurements from the local laboratory.

The subject's highest value during the investigational period will be used.

- ALT >3xULN, >5xULN, >8xULN, >10xULN, >20xULN
- AST >3xULN, >5xULN, >8xULN, >10xULN, >20xULN
- ALT or AST >3xULN, >5xULN, >10xULN, >20xULN
- ALP > 1.5 xULN
- Total Bilirubin >2xULN
- (ALT or AST >3xULN) and (Total Bilirubin >2xULN or INR > 1.5)
- (ALT or AST >3xULN) and ALP <2xULN and Total Bilirubin >2xULN

Note: ALT, AST, ALP and Total Bilirubin results will be classified using the reference ranges supplied by the local laboratories.

The last 2 criteria where 2 or more parameters are evaluated will be with the measurements on the same day or up to 1 day apart (Samples to be taken simultaneously or within a maximum of 24 hours).

The denominator for each criterion will be the number of subjects who have at least one value during the investigational period. The number and percentage of subjects meeting the criteria during the investigational period will be summarized by treatment group.

A scatter plot of Peak AST or ALT data vs. Peak Total Bilirubin data will be presented for mirabegron subjects. Data will be presented as fractions of the ULN (of the local laboratories). In this scatter plot the area for Hy's Law will be presented, where ALT or AST >3xULN and Total bilirubin

>2xULN (ALT, ALT and Total Bilirubin from same blood sample or within a maximum of 24 hours). The area for hyperbilirubinemia (ALT and AST <3xULN and Total bilirubin >2xULN), Temple's corollary (ALT or AST >3xULN and Total bilirubin < 2xULN) will also be presented in this scatter plot.

Laboratory data will be provided in listing format by site and subject for the SAF.

#### 6.5.3 Vital Signs

The baseline value will be the last non-missing value taken on or prior to first dose of study drug (Visit 2).

Vital signs (systolic blood pressure, diastolic blood pressure, and pulse rate and measurement for temperature) will be listed and summarized by treatment group and visit using mean, standard deviation, median, minimum and maximum. Additionally, for groups with both a baseline and a post-baseline 12 measurement, a within-subject change will be calculated per visit as the post-baseline measurement minus the baseline measurement and summarized by treatment group, total and visit. Summary of vital signs will be presented for each visit [visits 1, 2 (Baseline), 3, 4, and 5], and for EoT values.

Vital signs data will be provided in listing format by site and subject for the SAF.

#### 6.5.4 Electrocardiograms

The baseline value will be the last non-missing value taken on or prior to first dose of study drug. In the "Schedule of Assessment" table in the protocol (Table 1) this "baseline" assessment will be done at screening (Visit 1).

ECG variables will be summarized using mean, standard deviation, median, minimum, and maximum by treatment group total and visit, including changes from baseline for groups with both a baseline and week 12 measurement. Summary of ECG variables will be presented for each visit [visits 1 and 5], and for EoT values. In addition to the ECG variables mentioned in Section 5.4.5, QTcF (msec) (=QT (msec)/([RR (msec)/1000]1/3) will be summarized. Note: unit for QT and RR reported in CRF is msec.

Normal, not clinically significant abnormal, and clinically significant abnormal results as assessed by investigator for the 12 lead ECG along with shift tables will be presented for changes from baseline to Week 12 including local interpretation categories by the following treatment groups:

- Mirabegron 25 mg (Never Up-Titrated)
- Mirabegron 50 mg (As-Randomized)
- Total Mirabegron.

The QTc interval will be summarized using frequency tables for each treatment visit and time point for values of clinical importance using the range criteria below.

Category	QTc Interval Criteria Value (msec)	
Normal	$\leq$ 450	
Borderline	> 450	
Prolonged	> 480	
Clinically significant	> 500	

Note that these categories are cumulative in that subjects satisfying criterion for more extreme category will also be counted in each applicable less extreme category.

The corrected QT interval (i.e., QTcF) will also be summarized by treatment group and visit showing the frequencies of subjects with the following changes from baseline:

Variable	Change from Baseline
QTc Interval (msec)	< 0
	$\geq 0$ and $< 30$
	$\geq$ 30 and < 60
	$\geq$ 60

ECG data will be provided in listing format by site and subject for the SAF.

#### 6.5.5 Pregnancies

A detailed listing of all pregnancies will be provided if any occur using All Enrolled Set.

#### 6.5.6 Other Safety-Related Assessments

#### 6.5.6.1 Post Void Residual Volume

The baseline value will be the last non-missing value taken on or prior to first dose of study drug. In the "Schedule of Assessment" table in the protocol (Table 1) this "baseline" assessment will be done at screening (Visit 1).

PVR will be summarized by treatment group and visit using mean, standard deviation, median, minimum, and maximum at each treatment visit, including changes from baseline (for groups with both a baseline and week 12 measurement). In case of 2 measurements at the same visit, the lowest (instead of mean) PVR volume will be used for the calculations. Summary of PVR values will be presented for each visit [visits 1 and 5], and for EoT values.

PVR data will be provided in listing format by site and subject for the SAF.

## 6.6 Analysis of Pharmacokinetics

Not applicable.

### 6.7 Analysis of Pharmacodynamics

Not applicable.

### 6.8 Other Analyses

Not applicable.

### 6.9 Interim Analysis (and Early Discontinuation of the Clinical Study)

There is no planned interim analysis but a data cut with summaries (e.g., after 50% of subjects planned to be randomized have had their week 12/EoT assessment) and the planned primary analysis for the end of the study may be generated at a specific timepoint during the study for regulatory reporting purposes. No decisions regarding conduct of the study (i.e., stopping) will be based on these results.

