9.5 Interim Analysis

There is no planned interim analysis but a data cut with summaries and the planned primary analysis for the end of the study may be generated at a specific timepoint during the study for regulatory reporting purposes. No decisions regarding conduct of the study (i.e., stopping) will be based on these results.

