## 2.2 Study Design

[figure not shown]
The study follows an open-label, randomized, 12-week, prospective, interventional postauthorization design for the treatment of OAB in approximately 249 Chinese subjects. Each subject will participate in one 12-week treatment period.

This study is designed to support the Imported Drug License (IDL) renewal and mirabegron safety surveillance in China. The data-cut with summaries and the planned primary analysis for the end of this study will be used for IDL renewal. Subjects fulfilling the screening inclusion/exclusion criteria will be randomized in 2:1 ratio to 50 mg mirabegron and 25 mg mirabegron using a computer-generated randomization to reduce selection bias. Treatments will be administered once daily orally after meal during a 12-week, open-label treatment period. Study visits will take place at weeks 4, 8 and 12. For 25 mg mirabegron group, a dose escalation to 50 mg is permitted on visit 3 and visit 4 according to investigators' discretion.

Planned total number of study sites include approximately 10 study sites across China.

Figure 1 presents the study schema.

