A data cut with summaries and the planned primary analysis for the end of the study may be performed after 50% of subjects planned to be randomized have had their visit 5/week 12/EoT assessment, for regulatory reporting purposes. No decisions regarding conduct of the study (i.e., stopping) will be based on these results.

Details of the schedule of clinical assessments are available in the protocol.

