# 4 ANALYSIS SETS

In accordance with International Conference on Harmonization (ICH) recommendations in guidelines E3 and E9, the following analysis sets will be used for the analyses.

The determination of whether subjects are included or excluded from the safety and efficacy analysis sets will be made prior to database hard-lock for the primary report.

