# **6 STATISTICAL METHODOLOGY**

## 6.1 General Considerations

Continuous data will be summarized descriptively including the number of subjects (n), mean, standard error of the mean (SEM) (efficacy data), standard deviation (SD), median, minimum and maximum. Categorical data will be summarized by frequencies and percentages. Percentages by categories will be based on the number of subjects with no missing data, i.e., the percentages for the non-missing categories will add up to 100%.

All statistical comparisons will be conducted using 2-sided tests at the 5% significance level unless stated otherwise. All null hypotheses will be of no treatment difference, all alternative hypotheses will be two-sided, unless specifically stated otherwise.

All data summarization and analyses will be performed using SAS® Version 9.4 or higher on Linux. Specifications for table, figures, and data listing formats can be found in the TLF specifications.

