# 6.4 Analysis of Efficacy

Efficacy analysis of the data from Mirabegron 50 mg group will be conducted on the FAS, and interpretation of results from statistical tests will be based on the FAS as well.

No multiplicity adjustment will be necessary in this study.

Efficacy data will be summarized by visit (week 0, 4, 8 and 12) and by EoT values unless otherwise specified.

All inferential statistics will be presented by the following treatment groups:

- Mirabegron 25 mg (Total)
- Mirabegron 50 mg (As-Randomized)

All summary descriptive statistics will be presented by the following treatment groups:

- Mirabegron 25 mg
  - Never Up-Titrated
  - Later Up-Titrated to 50 mg
  - Total
- Mirabegron 50 mg
  - $\circ$  as Randomized
  - Up-Titrated from 25 mg
  - Total

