### 6.4.1.1 Primary Analysis for Primary Efficacy Endpoint

The primary estimator for the primary estimand as defined in [Section 2.1.1 Estimand] will be calculated according to the evaluation of the primary efficacy endpoint. The primary efficacy endpoint will be analyzed using a Mixed Models Repeated Measures (MMRM). The MMRM model will include visit (the repeated term), treatment group (25 mg [total] or 50 mg [as-randomized]), pooled site, sex and the interaction between treatment group and visit as fixed effects and baseline measurement (the mean number of micturitions per 24 hours) as covariate. The algorithm to pool sites will be generated and documented prior to data base lock (Appendix 9.1). If the inclusion of pooled sites creates modeling problems, then dropping that factor will be considered. Subject will be identified as subject in the repeated statement.

The hypothesis for comparisons is given as follows:

- H0: The adjusted mean change from baseline at week 12 in mean number of micturitions per 24 hours in the 50 mg group is not different from zero.
- H1: The adjusted mean change from baseline at week 12 in mean number of micturitions per 24 hours in the 50 mg group is not equal zero.

Statistical testing will be done 2-sided at a 5% significance level.

The MMRM model results will be presented by treatment least squares (LS) means ( $\pm$  standard error [SE]) along with 2-sided 95% confidence intervals (CIs) and associated p-value for mean changes from baseline at weeks 4, 8 and 12 (the primary endpoint). Data from subjects who switch from 25 to 50 mg mirabegron will not be included in MMRM model. Data from those subjects prior to switching will still be included in the MMRM model with treatment equal to 25 mg.

Model fitting will be visually assessed. A scatter plot of residuals versus predicted values, along with histogram and normal probability plots will be produced.

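### Does allowing the primary 5% test at an optional mid-study data cut as well as at the end inflate the type I error?

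*SAP*

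**What the plan says.** Protocol 9.5 and SAP 6.9 share a construction. The protocol begins "There is no planned interim analysis but a data cut with summaries and the planned primary analysis for the end of the study" and, like SAP 6.9, says that these may be produced partway through for regulatory reporting; in SAP 6.9 the words are "the planned primary analysis for the end of the study may be generated at a specific timepoint during the study for regulatory reporting purposes". Both add that no decision on conduct, such as stopping, will rest on the results.

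Timing differs by place. SAP 2.2, in the text after the study schema, says the cut "may be performed after 50% of subjects planned to be randomized have had their visit 5/week 12/EoT assessment". SAP 6.9 gives 50% only as an example, and Protocol 9.5 gives no timing.

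On use, SAP 2.2 and the protocol synopsis say: "The data-cut with summaries and the planned primary analysis for the end of this study will be used for IDL renewal".

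The primary analysis is a test. SAP 6.4.1.1 states a null hypothesis of zero adjusted mean change at week 12 in the 50 mg group and reports LS means "along with 2-sided 95% confidence intervals (CIs) and associated p-value for mean changes from baseline at weeks 4, 8 and 12". SAP 6.1 adds: "All statistical comparisons will be conducted using 2-sided tests at the 5% significance level unless stated otherwise". SAP 6.4 states: "No multiplicity adjustment will be necessary in this study".

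SAP 4 refers to a single lock: membership of the safety and efficacy analysis sets "will be made prior to database hard-lock for the primary report".

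**The concern.** Read together, these sections permit the same 5% test on accumulating data twice, with no division of alpha and with both outputs going into the renewal file. The one safeguard concerns how the study is run, not which p-value may be cited as evidence of efficacy. If a significant result at either look could be claimed, the 5% level would not cover the procedure. The 80% power is also stated for 125 evaluable subjects and would not describe a smaller cut. At stake would be the type I error of the only hypothesis test that the trial was sized for.

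**Working it through.** **Inputs.** From SAP 3 (same in Protocol 9.2): change 0.9, SD 3.562, two-sided 5%, 125 evaluable on 50 mg, 25% dropout, about 166 enrolled. From SAP 2.2: 249 subjects, 2:1 allocation. The 50% cut is from SAP 2.2 and, as an example, SAP 6.9.

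**1. The plan's own figure.** One-sample t-test, noncentrality = (0.9/3.562) × √n. At n = 125 this is 2.825, the critical value is 1.979, and power is 80.0%. At n = 124 power is 79.7%, so 125 is the exact t-test minimum. Dropout: 125/0.75 = 166.7, against about 166 stated, which is also two thirds of 249. The stated design reproduces.

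**2. Size of a 50% cut.** 0.50 × 249 ≈ 125 subjects in both arms, of whom two thirds, about 83, are on 50 mg.
- All 83 have a week 12 value and the final n is 125: fraction 83/125 = 0.664.
- The 25% dropout already applies: 0.75 × 83 ≈ 62, fraction 62/125 ≈ 0.50.

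These are headcount approximations. The MMRM also uses week 4 and week 8 data, so true information would differ somewhat.

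**3. Error if either look could count.** Under the null hypothesis the two statistics are bivariate normal with correlation √r, where r is the information fraction. The error is 1 − P(|Z₁| ≤ 1.96 and |Z₂| ≤ 1.96).

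| r | correlation | two-sided error | favourable direction only |
|---|---|---|---|
| 0.50 | 0.707 | 8.3% | 4.2% |
| 0.664 | 0.815 | 7.7% | 3.9% |
| 0.90 | 0.949 | 6.5% | 3.2% |

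A simulation of 4 million trials at r = 0.50 also gives 8.3%. The 0.90 row only shows the trend for a late cut; no document mentions that timing.

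**4. Error if only the end-of-study test counts.** P(|Z₂| > 1.96) = 5.0%, whether or not a cut is taken, because the cut neither stops the study nor alters the final analysis.

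**5. Power of a 5% test at the cut.** n = 62: noncentrality 1.990, power 50%. n = 83: noncentrality 2.302, power 62%.

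**6. Which rule do the documents support?** Step 3 needs two conditions: the cut is taken, and significance at either look may be claimed.
- The first is optional in all three places.
- The second is stated nowhere. The analysis is identified by name with the end of the study, and SAP 4 ties the analysis sets to one hard lock for the primary report.
- Protocol 2, 2.1 and 4.3 explain the purpose: the agency asked for further data on usage and starting dose in Chinese patients, to be handed in at renewal. Nothing makes renewal conditional on a significant result.

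Step 4 therefore describes the plan as written.

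**The case for a change.** The strongest reply is that silence is not a safeguard. SAP 6.9 moves forward a complete test, with a p-value at 5%, and SAP 2.2 puts the cut and the primary analysis side by side as renewal evidence without ranking them. One can read the SAP 2.2 sentence on renewal as a descriptive cut plus a separate end-of-study analysis. But the data-cut sentences in SAP 2.2 and 6.9 let both items be produced during the study, so the reading that places the test at the cut is the better one. A sentence naming the confirmatory test would be cheap, and SAP 1 allows revisions until hard lock.

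This much stands: no passage calls the cut descriptive, and the 80% power does not apply to it. What does not follow is that the test is uncontrolled. The 8.3% belongs to a claim rule that the documents do not contain.

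The possible remedies also gain little. Dropping the p-value at the cut changes nothing of substance, since a 95% CI that excludes zero is the same 5% test. Splitting alpha (O'Brien-Fleming at r = 0.50: 0.0052, then 0.0480) would leave the final look alone with 79.5% power at n = 125. It would also be doubtful as prespecification: SAP 9.1 records that 249 subjects had already been randomized at 15 sites when this version was written, and the study is open-label. A 50% cut may already lie in the past; the documents do not say whether one was made.

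**Conclusion.** The concern does not call for a change. Followed as written, the end-of-study analysis tests its null hypothesis at 5% with 80% power at 125 evaluable subjects, and an optional, non-stopping data report beforehand affects neither figure. The inflation to about 8.3% (fraction 0.50) or 7.7% (fraction 0.664) is conditional on an either-look rule that no section states and that the naming of the analysis, the single lock for the primary report and the data-submission purpose all point away from. What remains is an unwritten detail, namely that results at a cut are provisional and the final test is the confirmatory one. A competent analyst would supply it when writing the report.

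This rests on two assumptions: that nobody would present a significant result at the cut as the trial's efficacy conclusion, and that any cut leaves the conduct and analysis of the rest of the study untouched, as the plan says for conduct. Even if the first failed, the hypothesis concerned is only zero change from baseline within one open-label arm.

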### 6.10 Additional Conventions

#### 6.10.1 Analysis Windows

The study protocol gives the total study schedule and the permissible intervals for these visits expressed as the number of days relative to visit 2/baseline. The total time each subject will be in the study will not exceed 16 weeks with a maximum of a screening period of 2 weeks, a maximum of 12 weeks for the investigational period and a maximum of a follow-up period of 2 weeks.

Analyses will not exclude subject data due to the subject's failure to comply with the visit schedule, see Table 5.

The data summary by visits will be done following the analysis windows specified in Table 5.

For Bladder e-diary data. using the Subject Visit (SV) domain: for each diary record find the date from SV that satisfies the condition (Date from SV-7)  $\leq$  Diary Date  $\leq$  Date from SV. Using the corresponding relative day of that date, assign the analysis visit as specified in Table 5.

Analysis Visits	Target day relative to Baseline (Visit 2, Day 1)	Analysis Window (day)	
Bladder e-diary			
Baseline	Day -1	Day -12 to Day -1	
Week 4	Day 28	Day 7 to Day 42	
Week 8	Day 56	Day 43 to Day 70	
Week 12	Day 84	Day 71 to Day 97	
ЕоТ	Day 84	Day 2 to $\leq$ Last dose of study drug	

 Table 5
 Visit Windows for Efficacy and Safety Parameters

Analysis Visits	Target day relative to Baseline (Visit 2, Day 1)	Analysis Window (day)			
OABSS questionnaire					
Baseline	Day 1	Day -12 to Day 1			
Week 4	Day 28	Day 2 to Day 42			
Week 8	Day 56	Day 43 to Day 70			
Week 12	Day 84	Day 71 to Day 97			
ЕоТ	Day 84	Day 2 to $\leq$ Last dose of study drug			
Vital signs*					
Week -2	Day -14	Day -17 to Day -4			
Week 0/ Baseline	Last value prior to first dose	Day -3 to Day 1 (prior to first dose)			
Week 4	Day 28	Day 2 to Day 42			
Week 8	Day 56	Day 43 to Day 70			
Week 12	Day 84	Day 71 to Day 97			
ЕоТ	Day 84	Day 1 to $\leq$ Last dose of study drug			
ECG, Clinical Laboratory Tests (including Pregnancy Test) and PVR*					
Week -2/ Baseline	Day -14	Day -17 to Day 1 (prior to first dose)			
Week 12	Day 84	Day 2 to Day 97			
ЕоТ	Day 84	Day 1 to $\leq$ Last dose of study drug			

\* if an Early Discontinuation visit occurs within any specified visit window, all data collected during this visit will be assigned to the respective analysis visit.

For non-diary data, if a subject has more than one non-missing value within a visit window, the non-missing assessment which is closest to the target day within a window will be used. If two or more values are equally close and on different days, the latest non-missing value will be used. If two or more values are equally close and on the same day, the mean will be used for continuous variables or the worst observed case for categorical variables.

For diary data, the assessment date for the whole diary will be considered to be the date of the last valid day of the diary. If more than one diary has an assessment date within the same window, and if this results in more than one non-missing value of a diary variable, the non-missing value with the diary assessment day that is closest to the target day will be used. In case of ties on different days, the later non-missing value will be used. In case of ties located on the same side of the target day (i.e., more than one value for the same day), the mean of the values will be used for continuous variables and the worst value for categorical variables.

For analyzing diary data the labels of the study visits will not be used, they will be assigned based on the dates of assessment.

A two-day window around the visit date will be applied for the assignment of study period for exposure data.

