7.2.1 Laboratory Assessments

Clinical laboratory tests will be performed at a local laboratory.

Blood samples will be collected via a peripherally placed intravenous cannula or by direct venipuncture in a suitable forearm vein.

Blood samples for hematology and biochemistry and urine samples for urinalysis will be collected as indicated in the Schedule of Assessments [Table 1]. The clinical laboratory tests to be performed in the study are listed in [Section 10.6 Appendix 6 Laboratory Assessments].

A blood sample will be collected for serology tests (HAV antibodies [IgM], HBc antibodies, HBsAg, HCV antibodies, syphilis and antibodies to HIV) at screening only.

Urine pregnancy tests (female subjects only) will be performed according to the clinical site's preferred method. Pregnancy tests will be performed as indicated in the Schedule of Assessments [Table 1].

If any of the clinical laboratory tests results be outside the normal range at any scheduled time point during the study, the investigator may decide to repeat the test(s) on new samples. The clinical relevance of the abnormal results will be documented. Clinically relevant changes will be recorded as AEs (see [Section 7.3 Adverse Events and Other Safety Aspects]).

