10.4 Appendix 4: Liver Safety Monitoring and Assessment

The purpose of this appendix is to provide guidance for the monitoring of drug-induced liver injury during the course of the study. It should be noted that this section does not specify the end-of-study analyses of liver enzymes. The end-of-study liver enzymes analyses will be described in the SAP. Any subject enrolled in a study with active drug therapy and reveals an increase of serum aminotransferases (AT) to $> 3 \times$ ULN or bilirubin $> 2 \times$ ULN should undergo detailed testing for liver enzymes (including at least alkaline phosphatase [ALP], ALT, AST and TBL). Testing should be repeated within 72 hours of notification of the test results. For studies for which a local laboratory is used, alerts will be generated by the local laboratory regarding moderate and severe liver abnormality to inform the investigator and study team. Subjects should be asked if they have any symptoms suggestive of hepatobiliary dysfunction.

Definition of Liver Abnormalities

Confirmed abnormalities will be characterized as moderate and severe where ULN is as shown below.

	ALT or AST		TBL
Moderate	$> 3 \times ULN$	or	$> 2 \times ULN$
Severe	$> 3 \times ULN$	and†	$> 2 \times ULN$

Table 6Moderate and Severe Liver Abnormalities

ALT: alanine aminotransferase; AST: aspartate aminotransferase; TBL: total bilirubin; ULN: upper limit of normal

†Samples taken simultaneously or within maximum 24 hours.

In addition, the subject should be considered to have severe hepatic abnormalities for any of the following:

- ALT or $AST > 8 \times ULN$
- ALT or AST > $5 \times$ ULN for more than 2 weeks
- ALT or AST > 3 × ULN and † TBL > 2 × ULN or INR > 1.5 (if INR testing is applicable/evaluated)
- ALT or AST > $5 \times$ ULN and \dagger (TBL > $2 \times$ ULN in subjects with liver metastases)
- ALT or $AST > 3 \times ULN$ with the appearance of fatigue, nausea, vomiting, right upper quadrant pain or tenderness, fever, rash and/or eosinophilia (> 5%)

[†]Samples taken simultaneously or within a maximum of 24 hours.

The investigator may determine that abnormal liver function results, other than as described above, may qualify as moderate or severe abnormalities and require additional monitoring and follow-up.

Follow-up Procedures

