## 5.4.3 Clinical Laboratory Variables

Hematology, biochemistry and urinalysis assessments will be taken at visit 1/week -2 (screening), and visit 5/week 12 (EoT).

All clinical laboratory assessments will be performed at a local laboratory. Urine pregnancy tests (female subjects of childbearing potential only) will be performed according to the clinical site's preferred method at visit 1/week -2 (screening) and visit 5/week 12 (EoT) except for cases in which the possibility of pregnancy was clearly ruled out by hysterectomy, bilateral oophorectomy or the passage of 2 or more years after last menstruation.

A blood sample will be collected for serology tests (HAV antibodies [IgM], HBc antibodies, HBsAg, HCV antibodies, syphilis and antibodies to HIV types 1 and 2) at screening only.

Additional hematology, biochemistry and urinalysis (UA dipstick) tests may be performed at visit 1/week -2 (screening) and visit 5/week 12 (EoT). If any of the clinical laboratory tests results are outside the normal range at any scheduled time point during the study, the investigator may decide to repeat the test(s) on new samples. The clinical relevance of the abnormal results will be documented. Clinically relevant changes will be recorded as AEs (see Section 7.3 of protocol).

The laboratory parameters that will be assessed during the conduct of the study are listed in Table 4.

Hematology	Biochemistry	Urinalysis	Serology*
Hematocrit	Albumin	Leukocyte esterase	HAV antibodies
Hemoglobin	Alanine aminotransferase	Nitrites	(IgM)
Mean corpuscular volume	Alkaline phosphatase	pH	HBsAg
Mean corpuscular	Aspartate aminotransferase	Protein	HBc antibodies
hemoglobin	Bicarbonate	Red blood cells	HCV antibodies
Mean corpuscular	Blood urea nitrogen	Human chorionic	HIV antibodies
hemoglobin concentration	Calcium	gonadotropin (female	types 1 and 2
Platelets	Chloride	subjects only)	Syphilis
Red blood cell count	Corrected serum calcium		
White blood cell count	Creatinine		
White blood cell count	Creatinine kinase		
differential	Glucose		
	Lactate dehydrogenase		
	Magnesium		
	Phosphate		
	Potassium		
	Sodium		
	Total bilirubin (total and		
	direct)		
	Total protein		

Table 4Laboratory Assessments

\* Serology parameters will be only collected at screening.

The value of each hematology and biochemistry parameter will be compared to its normal range and classified as High, Low or Normal. Urinalysis parameters will be similarly classified as either Normal or Abnormal.

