Additionally, for groups with both a baseline and week 12 measurement (i.e., Mirabegron 25 mg [Never Up-Titrated], Mirabegron 50 mg [As-Randomized] and Total Mirabegron) a within-subject change will be calculated as the post-baseline measurement minus the baseline measurement and summarized in the same way. Each laboratory result will be classified as low (L), normal (N), or high (H) at each visit according to the laboratory supplied reference ranges.

The number and percentage of subjects below and above reference range will be summarized by treatment group and visit.

Frequency tabulations of qualitative clinical laboratory variables (urinalysis) will be presented by treatment group and visit.

Summary shifts of reference range (low, normal, high) changes from baseline to week 12 will be presented by the following treatment groups:

- Mirabegron 25 mg (Total)
- Mirabegron 50 mg (As-Randomized)
- Total Mirabegron, i.e., the sum of the Mirabegron 25 mg (Total) and of Mirabegron 50 mg (As-Randomized).

These shifts are categorized as:

- "Shift to Low": shift from normal or high to low
- "Shift to High": shift from normal or low to high
- "Categorized Increase": shift from low to normal or from normal to high
- "Categorized No Change": value stays in the same reference range
- "Categorized Decrease": shift from high to normal or from normal to low.

All clinical laboratory data collected during the study and variables derived from it will be listed using SAF.

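### The closest-to-Day-84 rule lets a repeat laboratory test replace the abnormal result that prompted it in the Week 12 out-of-range and shift tables

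*SAP*

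**What the plan says.** SAP 6.10.1, Table 5, groups "ECG, Clinical Laboratory Tests (including Pregnancy Test) and PVR" under one post-baseline visit, Week 12, with target Day 84 and window Day 2 to Day 97. This row has no last-dose limit; the separate EoT row does stop at the last dose. A footnote assigns Early Discontinuation visit data to whichever analysis visit's window they fall in.

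For several non-diary values in one window, SAP 6.10.1 states that "the non-missing assessment which is closest to the target day within a window will be used". It continues: "If two or more values are equally close and on different days, the latest non-missing value will be used". For equally close values on the same day, "the mean will be used for continuous variables or the worst observed case for categorical variables".

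On repeats, protocol 7.2.1 says that after an out-of-range result "the investigator may decide to repeat the test(s) on new samples", and SAP 5.4.3 repeats this. For liver elevations, protocol Appendix 4 adds: "Testing should be repeated within 72 hours of notification of the test results".

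The tables concerned are in SAP 6.5.2: counts below and above the reference range by group and visit, and "Summary shifts of reference range (low, normal, high) changes from baseline to week 12". The liver threshold table (SAP 6.5.2.1) works differently and takes each subject's maximum.

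**The concern.** The documents provide for a repeat when a result is out of range and give no corresponding reason to repeat a normal one. Under the closest-value rule an abnormal result can therefore be replaced by a normal repeat, but a normal result has no repeat to replace it. Sending ties to the later value pushes the same way.

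Visit 5 (or the withdrawal visit) is the only scheduled post-baseline laboratory draw. If its abnormal result is displaced, the subject's main on-study laboratory finding is missing from the out-of-range count and the shift table. In an early withdrawal the replacement may be an off-drug sample. Laboratory tests are a named secondary safety endpoint, and the study is meant to support safety surveillance, so understating new abnormalities matters even though the tables are descriptive.

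**Working it through.** The plan states no figure for this effect, so the check applies its rule day by day.

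**Inputs from the documents.** Window Day 2 to 97, target Day 84, closest value kept, later value on a tie (SAP 6.10.1). Visit 5 allowed ±3 days (protocol Table 1). Early withdrawals also have an EoT visit (protocol Table 1, footnote 11). Planned dropout 25% (SAP 3; 125/0.75 = 166.7, against the stated figure of about 166). 249 subjects randomized (SAP 9.1).

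**Rule.** Let the original be on day d and the repeat on a later day r. The repeat is kept if r ≤ 97 and |r − 84| ≤ |d − 84|. For d < 84 this means r − d ≤ 2(84 − d) and r ≤ 97.

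| Original on | Repeat that replaces it |
|---|---|
| Day 2 to 71 | any later day up to Day 97 |
| Day 72 to 83 | within 2(84 − d) days: Day 77, 14 days; Day 80, 8; Day 81, 6; Day 82, 4; Day 83, 2 |
| Day 84 or later | none |

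This assumes no other draw nearer Day 84. With values on Days 40, 45 (repeat) and 84, the Day 84 value is kept and neither of the others is used.

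**Early withdrawals, original on Day 2 to 80 (79 days).** Replaced on 79 of 79 days at each lag tested up to 8 days (1, 3, 5, 7, 8), 78 of 79 at 10 days, 76 of 79 at 14 and 72 of 79 at 21.

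**Completers.** Day 84 ± 3 gives Visit 5 on Days 81 to 87. The worked example in SAP 5.5.1 runs from 1 July (Day 1) to Visit 5 on 23 September, which is 31 + 31 + 23 = Day 85; ±3 then gives Days 82 to 88.

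| Repeat lag | Days 81–87 | Days 82–88 |
|---|---|---|
| 1 day | 3 of 7 | 2 of 7 |
| 3 days | 2 of 7 | 1 of 7 |
| 5 days | 1 of 7 | 0 of 7 |
| 7 days or more | 0 of 7 | 0 of 7 |

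The lags are assumptions. The documents set none, apart from the 72-hour rule for liver elevations.

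**Size.** Assume half of abnormal results are repeated and half of repeats are normal, so q = 0.5 × 0.5 = 0.25. Let c be the exposed share of completers and s the share of early withdrawals who give a sample. Take 25% early withdrawals (0.25 × 249 ≈ 62), all exposed if sampled, with visit days evenly spread and the same abnormality rate in both groups. Then

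loss = q(0.75c + 0.25s) / (0.75 + 0.25s).

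- c = 3/7, s = 1: 0.25(0.321 + 0.25) = 14%
- c = 2/7, s = 1: 0.25(0.214 + 0.25) = 12%
- c = 1/7, s = 1: 0.25(0.107 + 0.25) = 9%
- c = 0, s = 1: 0.25 × 0.25 = 6%
- c = 0, s = 0.5: 0.25 × 0.125 / 0.875 = 4%

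The loss is directly proportional to q.

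**The case against.** The best defence is that abnormal results are not hidden. Clinically relevant changes become AEs, every laboratory value is listed, liver thresholds use the maximum, and laboratory data are also summarised at EoT, where an off-drug repeat cannot enter. All of that is true, but none of it corrects the two tables at issue. AE recording depends on investigator judgement in an open-label study, listings are not summaries, and the shift table is specified for week 12 only. A withdrawal sample taken after the last dose also falls outside EoT.

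A second defence is that the Table 5 footnote protects Early Discontinuation data. It assigns those data to a visit but does not rank them above a later value; at best it leaves the question open.

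A third is that a single wide window is deliberate, because laboratory tests, ECG and PVR have only one scheduled post-baseline assessment. This stands. A reader might infer from the narrower vital-signs window (Day 71 to 97) that laboratory tests should match it. Doing so would drop pre-Day-71 withdrawal samples taken after the last dose from both Week 12 and EoT.

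A reader might also infer that the repeat always wins in early withdrawals. The rule does not support that. An original on Days 72 to 83 survives a slow repeat, a repeat after Day 97 does not count, and same-day values are averaged or taken at their worst. A subject who stops treatment but attends near Day 84 may also have both values displaced.

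**Conclusion.** The point holds as a defect in the value-selection rule. Nothing in SAP 6.10.1 stops a result-prompted repeat from replacing the abnormal value in the Week 12 out-of-range and shift tables, and the bias runs towards fewer abnormalities. For early withdrawals replacement is almost certain when the repeat is prompt, on a later day no later than Day 97, and no other draw lies nearer Day 84. For completers it is limited to draws before Day 84 with a quick repeat.

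The 4% to 14% range rests on the two assumed halves, the repeat lag and the share of early withdrawals who give a sample. A reader might take 14% as the expected loss, but under those assumptions it is the top of the range: it needs Visit 5 on Days 81 to 87, repeats within a day or two, and a sample from every early withdrawal. The 25% is itself a planning allowance for the 50 mg group, applied here to all subjects. The existence and direction of the bias do not depend on these figures. The efficacy analysis and the sample size are unaffected.

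**What to change.** In SAP 6.5.2, base the laboratory out-of-range and shift tables on the worst post-baseline value, with worst low and worst high taken separately and both scheduled and unscheduled samples included. Alternatively, keep the by-visit tables and add worst-value ones.

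In SAP 6.10.1, state that the scheduled Visit 5 value, or the Early Discontinuation visit value, takes precedence over an unscheduled repeat in by-visit laboratory, ECG and PVR tables. Keep the Day 2 to 97 window so that early-withdrawal samples are not lost.

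With either the precedence rule or worst-value selection, an abnormal original is replaced by its repeat in none of the scenarios above. The cost is SAP wording and minor programming; SAP section 1 allows revision before hard lock. Reported abnormality rates may rise slightly. No study procedure changes.
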